8.3 ADVERSE EVENTS AND SERIOUS ADVERSE EVENTS

8.3.1 DEFINITION OF ADVERSE EVENTS (AE)

An adverse event is any untoward or unfavorable medical occurrence in a human subject, including any abnormal sign (for example, abnormal physical exam or laboratory finding), symptom, or disease, temporally associated with the subject's participation in the research, whether or not considered related to the subject's participation in the research.

8.3.2 DEFINITION OF SERIOUS ADVERSE EVENTS (SAE)

An adverse event (AE) or suspected adverse reaction is considered "serious" if, in the view of either of the co-PIs, it results in any of the following outcomes: (1) death, (2) a life-threatening adverse event, (3) inpatient hospitalization or prolongation of existing hospitalization, (4) a persistent or significant incapacity or substantial disruption of the ability to conduct normal life functions, or (5) a congenital anomaly/birth defect.

Important medical events that may not result in death, be life-threatening, or require hospitalization may be considered serious when, based upon appropriate medical judgment, they may jeopardize the participant and may require medical or surgical intervention to prevent one of the outcomes listed in this definition.

8.3.3 CLASSIFICATION OF AN ADVERSE EVENT

8.3.3.1 SEVERITY OF EVENT

For adverse events (AEs) not included in the protocol defined grading system, the following guidelines will be used to describe severity.

- **Mild** – Events require minimal or no treatment and do not interfere with the participant's daily activities.
- **Moderate** – Events result in a low level of inconvenience or concern with the therapeutic measures. Moderate events may cause some interference with functioning.
- **Severe** – Events interrupt a participant's usual daily activity and may require systemic drug therapy or other treatment. Severe events are usually potentially life-threatening or incapacitating. Of note, the term "severe" does not necessarily equate to "serious".

8.3.3.2 RELATIONSHIP TO STUDY INTERVENTION

All adverse events (AEs) must have their relationship to study intervention assessed by the clinician who examines and evaluates the participant based on temporal relationship and his/her clinical judgment. The degree of certainty about causality will be graded using the categories below.

- **Related (Possible, Probable, Definite)** – The AE is known to occur with the study intervention, there is a reasonable possibility that the study intervention caused the AE, or there is a temporal relationship between the study intervention and event. Reasonable possibility means that there is evidence to suggest a causal relationship between the study intervention and the AE.
- **Not Related (Unlikely, Not related)** – There is not a reasonable possibility that the administration of the study intervention caused the event, there is no temporal relationship between the study intervention and event onset, or an alternate etiology has been established.

8.3.3.3 EXPECTEDNESS

Adverse events will be considered unexpected if the nature, severity, or frequency of the event is not consistent with the risk information previously described for the intervention. As the intervention for this study is a pain management clinical decision support module, inadequately managed pain, drug interactions or side effects related to pain medications are expected adverse events.

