Potential risks to patient participants are considered minimal. For patients in all study arms, there is a potential breach of privacy of individually identifying study data. To minimize this risk, no individually identifying patient information will be made available in publication or dissemination efforts. Results that are shared will be in aggregate form.

For patients whose providers are exposed to the CDS, there are several additional potential risks. First, the CDS may not display all relevant clinical information about the patient, as the CDS is limited to what is contained in the EHR. Second, it is possible that the CDS could erroneously attribute a condition or drug to a patient based on the EHR. In the design phase, the study team will seek and feedback from multiple sources to ensure that the content and CDS firing is as accurate and appropriate as possible. Before implementation, several investigators will review and test the CDS firing to optimize the information displayed. Provider training will inform providers of these limitations and offer strategies to further minimize these risks. Throughout the implementation phase, the study team will request feedback from providers using the CDS to identify any issues and modify the CDS, if needed.

Third, the CDS may be inappropriate for a given individual patient and, if applied without further checking the clinical status of a given patient, could lead to erroneous therapy, adverse events, disability, or death. However, the clinical recommendations are personalized based on the patient's medical problem list, allergies and current medications. The risk of untoward consequences from such clinical actions is considered minimal. Moreover, this potential risk is routinely present in every clinical encounter in the health care system. Fourth, the potential shift in provider prescribing and/or pain management recommendations may also have unintended consequences on patients' post-procedure pain management. It is possible that this shift could cause under-controlled pain. Providers encounter this in current dental practice and will address it in a similar fashion consistent with the reasonable standard of care.

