8.3.4 TIME PERIOD AND FREQUENCY FOR EVENT ASSESSMENT AND FOLLOW-UP

Since there are no routine research contacts for all eligible patient participants, we will collect information from the electronic health record about hospitalizations, emergency department visits, observational bed, and subsequent opioid prescribing made within 3 days post-extraction procedure. This is consistent with the usual care delivery pathways and workflows related to dental procedures.

For the sub-sample of patients reached as part of survey data collection, CESR staff provides information to call their dental provider with questions or concerns. In this manner, the study team will not interfere with existing patient-provider communication, but rather support usual care.

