8.4 UNANTICIPATED PROBLEMS

8.4.1 DEFINITION OF UNANTICIPATED PROBLEMS (UP)

The Office for Human Research Protections (OHRP) considers unanticipated problems involving risks to participants or others to include, in general, any incident, experience, or outcome that meets all of the following criteria:

- Unexpected in terms of nature, severity, or frequency given (a) the research procedures that are described in the protocol-related documents, such as the Institutional Review Board (IRB)-approved research protocol and informed consent document; and (b) the characteristics of the participant population being studied;
- Related or possibly related to participation in the research (“possibly related” means there is a reasonable possibility that the incident, experience, or outcome may have been caused by the procedures involved in the research); and
- Suggests that the research places participants or others at a greater risk of harm (including physical, psychological, economic, or social harm) than was previously known or recognized.

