8.4.2 UNANTICIPATED PROBLEM REPORTING

The study team member or dental clinic staff will report unanticipated problems (UPs) to Co-investigator [name] or PI [name]. They will submit to Co-investigator [name] to collect and to aggregate. The PI [name] will be responsible for ensuring the assigned Institutional Review Board (IRB) receives notification in accordance with HPI Research Subjects Protection Program Standard Operating Procedures at the time of the event. The UP report will include the following information:

- Protocol identifying information: protocol title and number, PI's name, and the IRB project number;
- A detailed description of the event, incident, experience, or outcome;
- An explanation of the basis for determining that the event, incident, experience, or outcome represents an UP;
- A description of any changes to the protocol or other corrective actions that have been taken or are proposed in response to the UP.

To satisfy the requirement for prompt reporting, UPs will be reported using the following timeline:

- UPs that are serious adverse events (SAEs) will be reported to the IRB and to NIDCR within one week of the investigator becoming aware of the event.

- All UPs should be reported to appropriate institutional officials (as required by an institution's written reporting procedures), the supporting agency head (or designee), and the Office for Human Research Protections (OHRP) within one month of the IRB's receipt of the report of the problem from the investigator.

All unanticipated problems will be reported to NIDCR's centralized reporting system via Rho Product Safety:

- (1) Product Safety Fax Line (US): [name]
- (2) Product Safety Fax Line (International): [contact]
- (3) Product Safety Email: [contact]

General questions about SAE reporting can be directed to the Rho Product Safety Help Line (available 8:00AM – 5:00PM Eastern Time):

- (1) US: [name]
- (2) International: [contact]

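### The expectedness rule lists three kinds of harm as expected without a severity or frequency bound, and most of the safety data bearing on poorly controlled pain have no stated analysis

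*Combined protocol and SAP*

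**What the plan says.** Section 8.3.3.3 has two sentences. The first sets a general test: "Adverse events will be considered unexpected if the nature, severity, or frequency of the event is not consistent with the risk information previously described". The second, noting that the intervention is a decision-support module, concludes that "inadequately managed pain, drug interactions or side effects related to pain medications are expected adverse events". It gives no severity or frequency limit.

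Section 8.4.1 requires an unanticipated problem to meet three criteria together. The first is being "Unexpected in terms of nature, severity, or frequency given (a) the research procedures that are described in the protocol-related documents". Under 8.4.2, "UPs that are serious adverse events (SAEs) will be reported to the IRB and to NIDCR within one week" of the investigator learning of the event.

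The described risks are in 2.3.1. Decision-support content applied without checking the patient's status "could lead to erroneous therapy, adverse events, disability, or death". On the change in prescribing, the section says: "It is possible that this shift could cause under-controlled pain". It gives no rate for either.

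Sections 8.2 and 8.3.4 draw four items from the health record within 3 days of extraction: hospital admissions, emergency visits, observation-bed stays and later opioid prescriptions. Section 7.1 plans quarterly chart review of hospitalizations within 72 hours, and 9.4.4 summarizes those hospitalizations by arm. Patient-rated pain at days 3 to 6 is the H4 endpoint, analysed descriptively in 9.4.3. For patients reached by the survey, 8.3.4 says that "CESR staff provides information to call their dental provider with questions or concerns".

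**The concern.** The listed categories are the harms this intervention could most plausibly cause: pain left uncontrolled after a move away from opioids, and interactions or side effects from the alternative analgesics. If someone classifying an event applies the list literally, a serious interaction is expected because of its category. It then fails the first criterion in 8.4.1, and the one-week notice to the IRB and NIDCR is not triggered.

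The same harms also need to be visible in aggregate, because frequency cannot be judged from a single report. Poorly controlled pain would show mainly as an emergency visit, another opioid prescription or a high survey score. None of these appears in the stated safety analysis. An excess in an intervention arm that did not lead to admission could go unremarked in the safety tables.

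**Working it through.** **Expectedness.** Most of this check is textual.

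1. The general test in 8.3.3.3 compares an event with the described risk information. The list that follows is unbounded, and the section does not say which sentence governs when they conflict.
2. Severity: the described risk in 2.3.1 already extends to disability and death. A very severe interaction can be argued to be consistent with it.
3. Frequency: neither 2.3.1 nor 8.3.3.3 gives a rate for any listed category. The nearest thing is the statement that the risk of untoward consequences is minimal.
4. An event classed as expected fails criterion 1 of 8.4.1. All criteria must be met, so 8.4.2 does not apply to it.

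**Collected against analysed.**

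| Item | Collected | Stated safety review or analysis |
|---|---|---|
| Hospitalization | 8.2, 8.3.4 | 7.1 chart review; 9.4.4 by arm with 95% CI |
| Emergency visit | 8.2, 8.3.4 | none |
| Observation-bed stay | 8.2, 8.3.4 | none |
| Later opioid prescription | 8.2, 8.3.4 | none |
| Survey pain rating | survey, H4 | none (descriptive endpoint in 9.4.3) |

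Three of the four record-based items have no stated use. The amendment history (10.4) shows that these three were added on a DSMB recommendation.

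**Size of the pain data.** Section 9.2 gives 1,520 patients approached and a 79% response rate: 1,520 × 0.79 = 1,200.8, which reproduces the stated 1,200. Spread evenly over arms (an assumption), 1,200 / 3 = 400 per arm. Coverage of intervention-period patients is 1,200 / 8,400 = 14% to 1,200 / 6,900 = 17%.

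**What a by-arm pain table could show.** The documents give neither a severe-pain rate nor an ICC for pain, so the following inputs are assumptions for illustration: severe pain in 10% against 16% (average p = 0.13), n = 400 per arm, and 51 / 3 = 17 providers per arm, so m = 400 / 17 = 23.5 surveys per provider.

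SE = √{2p(1 − p)/n × [1 + (m − 1) × ICC]}

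- ICC 0.02: factor 1.45, SE 0.0286, z = 0.06 / 0.0286 = 2.1
- ICC 0.05: factor 2.125, SE 0.0347, z = 1.73
- ICC 0.10: factor 3.25, SE 0.0429, z = 1.40

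Even with all surveys in hand, a 6-point excess clears 1.96 only at the lowest of these ICCs, and a mid-trial report would have fewer surveys. The table is worth having as a description with an interval. It is not a powered safety test.

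**The case against.** A reader might infer that no listed event can ever become an unanticipated problem. The documents do not support that. The first sentence of 8.3.3.3 and the first criterion in 8.4.1 both keep severity and frequency as grounds for calling an event unexpected, and the list does not say it overrides them. The mention of disability and death in 2.3.1 concerns decision-support content applied without checking, and the same paragraph calls the risk minimal, which is a loose benchmark. Under-controlled pain is described separately, without those outcomes. This defeats the absolute reading. It does not remove the ambiguity, because nothing tells the person classifying an event how the list and the test fit together.

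A reader might also infer that poorly controlled pain has no safety data route. That is wrong too. Emergency visits and later opioid prescriptions are collected to identify potential adverse events and are reasonable proxies. Sections 8.3.6 and 8.4.2 give dental providers and clinic staff reporting routes, and 8.2 adds feedback on the decision support. The gap is in stated review and analysis.

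Other safeguards count. Under 8.3.6, serious events go to the principal investigator as soon as possible, with those judged necessary reported under institutional procedures at the time of the event. Hospitalization rates are compared at least quarterly (7.1). Section 10.1.6 has the DSMB see safety and efficacy data by arm at least twice a year, so it may see H4 pain, although nothing supplied commits to that. The expectedness wording was revised on funder-side feedback (10.4), so it was deliberate, but that does not supply the missing bound.

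**Conclusion.** The point holds as a gap in wording and in the safety analysis. The two sentences of 8.3.3.3 can be read against each other, and on the literal reading a serious event in any of three categories is expected and escapes the one-week rule. Three of the four safety items collected, and about 1,200 pain ratings, have no stated safety analysis, although 2.3.1 names under-controlled pain as a possible harm. It should be corrected, but it does not show that such events must go unreported or that pain is unmonitored.

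This rests on the supplied text alone. The Data Safety Monitoring Plan and the DSMB charter may already contain some of these provisions. The figure of 400 ratings per arm assumes an even spread, and the z values of 1.40 to 2.1 rest wholly on assumed rates and ICCs, so no claim of detectability should be drawn from them.

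**What to change.** In 8.3.3.3, reconcile the two sentences: state that listed events are expected only within the severity and frequency described in the protocol, that each serious event is assessed individually for expectedness, and that frequency is judged from by-arm aggregates. Two simpler rules would not work. Making every serious event unexpected confuses seriousness with expectedness. Calling an event unexpected whenever its rate exceeds the Standard Practice rate cannot classify a single event and would be tripped by chance.

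In 9.4.4, summarize by arm all four items collected under 8.2 and 8.3.4, together with survey pain: the mean difference with its confidence interval, and the share above a cut-off that the DSMB sets in advance. Include these in the semiannual DSMB reports, and align 7.1 with the same list. Any statement of what the pain table can detect should be omitted or shown over a range of ICCs.

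Before amending, check the Data Safety Monitoring Plan and DSMB charter and cite any provision already there. The cost is protocol wording, one table from data already collected, and possibly a few more expedited reports.

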8.3.4 TIME PERIOD AND FREQUENCY FOR EVENT ASSESSMENT AND FOLLOW-UP

Since there are no routine research contacts for all eligible patient participants, we will collect information from the electronic health record about hospitalizations, emergency department visits, observational bed, and subsequent opioid prescribing made within 3 days post-extraction procedure. This is consistent with the usual care delivery pathways and workflows related to dental procedures.

For the sub-sample of patients reached as part of survey data collection, CESR staff provides information to call their dental provider with questions or concerns. In this manner, the study team will not interfere with existing patient-provider communication, but rather support usual care.

8.3.5 ADVERSE EVENT REPORTING

PI [name] or his designee will report necessary AEs in accordance with HPI Research Subjects Protection Program Standard Operating Procedures at the time of the event. More details about reporting are outlined in the DIODE Data Safety Monitoring Plan.

8.3.6 SERIOUS ADVERSE EVENT REPORTING

Any AE considered serious by a dental provider, study investigator, or PI, or which meets the definition of an SAE included in Section 8.3.2, Definition of Serious Adverse Events must be submitted to PI [name], as soon as possible.

PI [name] or his designee will report necessary SAEs in accordance with HPI Research Subjects Protection Program Standard Operating Procedures at the time of the event. More details about reporting are outlined in the DIODE Data Safety Monitoring Plan.

8.3.7 REPORTING EVENTS TO PARTICIPANTS

Not applicable

8.3.8 EVENTS OF SPECIAL INTEREST

Not applicable

8.3.9 REPORTING OF PREGNANCY

Not applicable

8.4 UNANTICIPATED PROBLEMS

8.4.1 DEFINITION OF UNANTICIPATED PROBLEMS (UP)

The Office for Human Research Protections (OHRP) considers unanticipated problems involving risks to participants or others to include, in general, any incident, experience, or outcome that meets all of the following criteria:

- Unexpected in terms of nature, severity, or frequency given (a) the research procedures that are described in the protocol-related documents, such as the Institutional Review Board (IRB)-approved research protocol and informed consent document; and (b) the characteristics of the participant population being studied;
- Related or possibly related to participation in the research (“possibly related” means there is a reasonable possibility that the incident, experience, or outcome may have been caused by the procedures involved in the research); and
- Suggests that the research places participants or others at a greater risk of harm (including physical, psychological, economic, or social harm) than was previously known or recognized.

8.4.2 UNANTICIPATED PROBLEM REPORTING

The study team member or dental clinic staff will report unanticipated problems (UPs) to Co-investigator [name] or PI [name]. They will submit to Co-investigator [name] to collect and to aggregate. The PI [name] will be responsible for ensuring the assigned Institutional Review Board (IRB) receives notification in accordance with HPI Research Subjects Protection Program Standard Operating Procedures at the time of the event. The UP report will include the following information:

- Protocol identifying information: protocol title and number, PI's name, and the IRB project number;
- A detailed description of the event, incident, experience, or outcome;
- An explanation of the basis for determining that the event, incident, experience, or outcome represents an UP;
- A description of any changes to the protocol or other corrective actions that have been taken or are proposed in response to the UP.

To satisfy the requirement for prompt reporting, UPs will be reported using the following timeline:

- UPs that are serious adverse events (SAEs) will be reported to the IRB and to NIDCR within one week of the investigator becoming aware of the event.

- All UPs should be reported to appropriate institutional officials (as required by an institution's written reporting procedures), the supporting agency head (or designee), and the Office for Human Research Protections (OHRP) within one month of the IRB's receipt of the report of the problem from the investigator.

All unanticipated problems will be reported to NIDCR's centralized reporting system via Rho Product Safety:

- (1) Product Safety Fax Line (US): [name]
- (2) Product Safety Fax Line (International): [contact]
- (3) Product Safety Email: [contact]

General questions about SAE reporting can be directed to the Rho Product Safety Help Line (available 8:00AM – 5:00PM Eastern Time):

- (1) US: [name]
- (2) International: [contact]

8.4.3 REPORTING UNANTICIPATED PROBLEMS TO PARTICIPANTS

Not applicable

9 STATISTICAL CONSIDERATIONS

9.1 STATISTICAL HYPOTHESES

- Primary Efficacy Endpoint(s):

H1 (alternative): Providers in the CDS and CDS-E strategy arms will reduce their likelihood of prescribing opioids for patients following extractions more than providers in the SP arm.

H1 endpoint: Comparison across study arms of the differential change in percentage of permanent tooth extraction encounters having an associated opioid prescription on the day of the extraction encounter, from the one year prior to the intervention implementation to one year after the intervention implementation.

- Secondary Efficacy Endpoint(s):

H2 (alternative): Providers in the CDS and CDS-E strategy arms will increase their likelihood of prescribing or recommending non-opioid analgesics at the extraction encounter and not prescribing opioids for patients following extractions more than providers in the SP arm.

H2 endpoint: Comparison across study arms of the differential change in percentage of permanent tooth extraction encounters having both 1) a prescription or recommendation in the treatment plan for non-opioid analgesics and 2) to not have an associated opioid prescription on the day of the extraction encounter, from the one year prior to the intervention implementation to one year after the intervention implementation.

H3 (alternative): Patients will report higher levels of the extent of shared decision making in the CDS-E arm than the CDS or SP arms.

H3 endpoint: Comparison across study arms of the mean of the 3-item composite of adapted Collaborate Shared Decision Making score reported by the patient.

H4 (descriptive): Compare patient report of average pain in the week following extraction across the 3 study arms.

H4 endpoint: Comparison across study arms of the mean pain rating in the 3-6 days since the extraction encounter, self-reported by patients.

